5.1. STATISTICAL ANALYSIS PLAN

5.1.1. Primary Hypothesis

Among infants receiving an opioid (defined as morphine or methadone) as the primary treatment for neonatal opioid withdrawal syndrome (NOWS), a rapid-wean intervention will reduce the days of opioid treatment from the first weaning dose to cessation of opioid compared to a slow-wean intervention.

5.1.2. Secondary Outcomes

Secondary Efficacy Outcomes.

Secondary Outcome 1: Compare the numbers of days of opioid treatment from the first weaning dose to cessation of opioid with a rapid- and slow-wean intervention among infants treated with morphine.

Secondary Outcome 2: Compare the numbers of days of opioid treatment from the first weaning dose to cessation of opioid with a rapid- and slow-wean intervention among infants treated with methadone.

Secondary Outcome 3: Compare the proportions of infants in the rapid- and slow-wean intervention arms who have an escalation or resumption of opioid during weaning.

Secondary Outcome 4: Compare the total amounts of opioid from the first weaning dose to cessation of opioid among infants in the rapid- and slow-wean intervention arms.

Secondary Outcome 5: Compare the proportion of infants who experience initiation and/or escalation of second- or-third line drugs to treat NOWS signs from the first weaning dose to cessation of opioid in the rapid- and slow-wean intervention arms.

Secondary Safety Outcome.

Secondary Outcome 6: Compare the proportion of infants in each intervention arm with safety outcomes of seizures (clinical or EEG), excessive stool output, respiratory disturbances, and feeding tolerance.

Other Secondary Outcomes.

Secondary Outcome 7: Compare the proportion of infants in each treatment intervention arm with an atypical neurobehavioral profile prior to discharge on the NICU Network Neurobehavioral Scale (NNNS).

Secondary Outcome 8: Compare the lengths of hospital stay for each treatment intervention arm.

Secondary Outcome 9: Determine assessments of maternal well-being and maternal-infant attachment in each intervention arm.

Secondary Outcome 10: Assessments of growth in each intervention arm.

Secondary Outcome 11: Assessment of infant wellness after discharge and until 24 months of age in each intervention arm.

Secondary Outcome 12: Assessment of infant development to 24 months of age in each intervention arm.

5.1.3. Other Collected Data

Initial descriptive analyses will include weaning intervention group characteristics. We will collect data to characterize the following.

- Stratification data
- Hospital variables: participation in ESC
- Maternal variables (e.g., socioeconomic status, obstetric complications, opioid medication, medication assisted treatment program, non-opioid drugs, cigarettes, alcohol, selective serotonin reuptake inhibitors, and psychiatric diagnoses)
- Infant demographics at birth (e.g., gestational age, birth weight, sex, multiples, growth parameters, out-born, and location of care)
- Characteristics of NOWS treatment (e.g., stabilization dose, age at stabilization, use of adjunctive drugs to the primary NOWS drug treatment)
- Infant characteristics at the start of the intervention (e.g., weight, postnatal age) and when medically ready for discharge per the hospital standard.

We will include the stratification variable (hospital) in regression modeling as a random effect, and we will include stabilization dose and maternal treatment as covariates. With respect to maternal treatment, it will be a categorical variable with four categories:

- 1) Methadone use
- 2) Buprenorphine \pm naloxone
- 3) Prescribed opioids other than methadone and buprenorphine \pm naloxone
- 4) Non-prescribed opioids

There will be some mixing among these four groups; therefore, we will use the following rules to classify infants:

- If methadone is used with other opioids, classify as methadone.
- If buprenorphine is used with other opioids, classify as buprenorphine \pm naloxone.
- If methadone is used with buprenorphine, classify based on which drug has been in use for a longer time interval.

Depending on the descriptive comparisons across weaning intervention groups, we may add other variables to the regression models such as medication assisted treatment programs. If the difference of a variable across the weaning intervention is statistically significant at a two-sided alpha of 0.05, then we may include the variable as a covariate in the regression models. Beyond the significant difference, we will consider other factors, such as the type of analysis, correlation with other variables in the model, and trial subcommittee discussion about the nature of the potential covariate.

5.1.4. Analysis of the Primary Hypothesis and Outcome

We will determine the outcome of the primary hypothesis on an intention to treat basis. We will assign infants who exit the intervention at 35 days of methadone/morphine treatment either as 35 days of opioid treatment or we will treat them as a censored value at 35 days. We will determine intervention differences of two means by analyzing the average number of days of opioid treatment from the first

weaning dose to cessation of opioid treatment. We will analyze the data using regression models that will include the intervention as a fixed effect and will include maternal treatment and stabilization dose as covariates. We will include site (hospital) in the model as a random effect. The primary test of interest will be the F-test of the intervention effect, and we will report the intervention difference along with 95% confidence interval (CI).

Because of possible censoring and removal of participants due to intervention failure, we will conduct sensitivity analysis of the primary outcome using several methods. The first sensitivity analysis will replicate the analysis, described above, and include other covariates in the model that were significantly different across the two weaning intervention groups. Sensitivity analyses will also be conducted to evaluate the effects of infants who were and were not part of the Eat Sleep Console trial as a covariate or effect modifier (see **Section 5.2.2**). Another possible sensitivity analysis will include non-parametric and/or survival regression (e.g., negative binomial, median regression, or survival analyses), as there is potential for skewness and censoring in the primary outcome.

Finally, sensitivity analysis will include fitting a competing risks model to the data where the possible competing risk states are weaned, parental withdrawal, physician withdrawal, and treatment failure (unable to wean by 35 days of methadone/morphine treatment). We will fit Cox proportional hazards models to the data to estimate the intervention effect and other covariate effects on “cause-specific hazards.” The analysis of the “cause-specific hazards” will allow for additional inquiry into the intervention effect on the primary outcome while accounting for competing safety and withdrawal risks.

Descriptive statistics (means, medians, SD, percentiles) for number of days of opioid treatment from the first weaning dose to cessation of opioid treatment will be generated and summarized in a table by treatment group.

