- We will provide each hospital’s pharmacy a dosing calculator (**Appendix 8**). After randomization, the pharmacy will input the weaning intervention (wean by 10% or 15% of the stabilization dose), the stabilization dose (mg/kg/day), the infant’s weight, and the dosing interval (every 3, 4, 8, or 12 hours) to identify the steps of the intervention arm. The dosing calculator will provide the absolute dose (mg) at each step of the intervention arm.
- Frequency of dose changes for **weaning**:
 - We will encourage clinical teams to wean study drug at least every 24 hours.
 - Clinical teams may wean infants at ≤ 24 hours of a given dose (< 8 doses when given every 3 hours, < 6 doses when given every 4 hours, < 3 doses when given every 8 hours and < 2 doses when given every 12 hours), per hospital guideline.
 - Infants not weaned by 24 hours of a given dose will enter a 12-hour period of study protocol guidelines (**Figure 4**). During this 12-hour period, the clinical team **must** wean infants who do not meet hospital specific criteria for escalation. Hospitals do not need to use the total 12-hour period to either wean or escalate if the infant meets the criteria prior to 12 hours. The research team will use dedicated in-services for all clinical teams of participating hospitals prior to study start on the specifics of the trial intervention including the 12-hour study protocol guideline.
 - The clinical team will order, “wean opioid per protocol” to trigger weaning.

[figure not shown]

Figure 4. Overview of the Time Periods Used by Clinical Team to Either Wean or Escalate Study Drug. A 24-hour period for weaning or escalation, per hospital guidelines (light blue bar). Multiple vertical green lines represent dosing intervals; in this example the infant is receiving an opioid every 3 hours. If the opioid dose does not change after 24 hours of dosing, the infant enters a 12-hour period of study protocol guideline (purple bar) to ensure that hospitals either wean or escalate and do not remain on the same dose. This approach will be applied to both weaning interventions.

- Frequency of dose changes for **escalation**:
 - Clinical teams may escalate the opioid at any time during the study intervention based on hospital guidelines; clinical teams do not need to wait for 24 hours of dosing.
 - The clinical team will order, “Escalate opioid per protocol” to initiate escalation.

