APPENDIX 10. PLACEBO DOSE UTILIZATION TO MAINTAIN THE BLIND IN THE RAPID-WEAN INTERVENTION

All infants that are randomized to the rapid-wean intervention will need to complete three placebo dose levels to maintain the blind (Appendices 4-7). Placebo administration only occurs after the infant has weaned from the 25% of stabilization dose level. We will consider a placebo dose level complete if the infant meets the following two criteria:

- 1) The infant tolerates the placebo without NOWS signs prompting a resumption of opioid.
- 2) The clinical team starts the next dose level in the intervention (i.e., the clinical team orders “wean opioid.”). If during a placebo dose the clinical team orders “escalate opioid”, then we will not consider the placebo dose complete. The clinical team needs to repeat a placebo dose that is not complete.

For infants who experience the same number of escalations or resumptions, placebo use in the rapid-wean intervention will result in study drug discontinuation after the same number of study steps as infants in the slow-wean intervention. Examples below demonstrate how placebo use in the rapid-wean intervention will maintain the blind (infant A). These examples include an infant without escalations (example A), an infant who has two escalations prior to reaching placebo (example B), an infant with one escalation that occurs during a placebo dose level (example C), an infant with two escalations: one that occurs during an opioid dose level and one that occurs during a placebo dose level (example D), and an infant with two escalations that both occur during the placebo levels (example E). For each example, we show an infant randomized to the slow-wean intervention with an identical number of escalations or resumptions of opioid (infant B).

We present the examples in terms of steps (not dose levels) to illustrate that there will be more study steps than dose levels when there are escalations of the opioid. In the examples, every infant randomized to the rapid-wean intervention needs to complete three placebo dose levels. We will consider placebo dose levels incomplete if opioid resumption interrupts them. The three placebo dose levels do not need to occur consecutively. For the research team to consider a placebo level complete, it needs to lead to a successful wean to another placebo level or off study drug.

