Title: Pragmatic, Randomized, Blinded Trial to Shorten Pharmacologic Treatment of Newborns with Neonatal Opioid Withdrawal Syndrome (NOWS)

Sponsor: National Institutes of Health

A			B		
	Infant A	Infant B		Infant A	Infant B
	Rapid wean:	Slow wean:		Rapid wean:	Slow wean:
	15 % of stabilization dose	10 % of stabilization dose		15 % of stabilization dose	10 % of stabilization dose
Stabilization Dose	100	100	Stabilization Dose	100	100
Step 1	85	90	Step 1	85	90
Step 2	70	80	Step 2	70	80
Step 3	55	70	Step 3	85	90
Step 4	40	60	Step 4	70	80
Step 5	25	50	Step 5	85	90
Step 6	Placebo*	40	Step 6	70	80
Step 7	Placebo*	30	Step 7	55	70
Step 8	Placebo*	20	Step 8	40	60
Key:			Step 9	25	50
Placebo Step			Step 10	Placebo*	40
Dose Medication is discontinued			Step 11	Placebo*	30
			Step 12	Placebo*	20
			Key:		
			Placebo Step		
			Dose Medication is discontinued		
			Escalation		

A. No Escalations. Infant A stops opioid at step 5. Infant B continues opioid until step 8. To maintain the blind, infant A receives placebo for steps 6-8. Both infants stop receiving “opioid/study drug” at step 8. **B. Two Escalations during Opioid Steps.** Both infants escalate at steps 3 and 5. Infant A discontinues opioid at step 9. Infant B discontinues opioid at step 12. Infant A receives 3 steps of placebo (10-12) to preserve blind. Both infants discontinue “study drug” at step 12.

C			D		
	Infant A	Infant B		Infant A	Infant B
	Rapid wean:	Slow wean:		Rapid wean:	Slow wean:
	15 % of stabilization dose	10 % of stabilization dose		15 % of stabilization dose	10 % of stabilization dose
Stabilization Dose	100	100	Stabilization Dose	100	100
Step 1	85	90	Step 1	85	90
Step 2	70	80	Step 2	70	80
Step 3	55	70	Step 3	55	70
Step 4	40	60	Step 4	40	60
Step 5	25	50	Step 5	25	50
Step 6	Placebo*	40	Step 6	40	60
Step 7	Placebo*	30	Step 7	25	50
Step 8	25	40	Step 8	Placebo*	40
Step 9	Placebo*	30	Step 9	25	50
Step 10	Placebo*	20	Step 10	Placebo*	40
Key:			Key:		
Placebo Step			Placebo Step		
Dose Medication is discontinued			Dose Medication is discontinued		
Escalation			Escalation		
Incompleted Placebo Step			Incompleted Placebo Step		
Escalation from Previous Dose and Discontinue			Escalation from Previous Dose and Discontinue		

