6.4.5 Sensitivity Analysis

Because of censoring and/or partial data collected on withdrawn infants we will perform the following additional analyses:

- 1. Replicate the primary analysis (H1) to include maternal treatment, stabilization dose, and maternal feeding.
- 2. Given the learning curves needed to be successful at this trial, we will run a sensitivity analysis limited to centers that enrolled greater than 10 infants.
- 3. Replicate the primary outcome analysis to evaluate the effect of being part of Eat Sleep Console
- 4. Perform survival analysis using cutoff at 35 days as censoring indicator.
- 5. If sample size allows, competing risk analysis will be performed using Cox proportional hazard model adjusting for the following: parental withdrawal, physician withdrawal, and treatment failure defined as unable to wean by 35 days of methadone/morphine treatment. This analysis will allow for additional inquiry into the intervention effect on the primary outcome while accounting for competing safety and withdrawal risks.
- 6. For H13, perform a sensitivity analysis for all hypotheses by removing follow ups outside the 22-26 weeks window.

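### The planned Cox hazard ratio does not suit a five-level versus eight-level weaning schedule; the survival sensitivity analysis should be stated in days, and a proportional-hazards check added

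*Protocol*

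**What the plan says.** **Competing risks.** Protocol 5.1.4 lists four competing states (weaned, parental withdrawal, physician withdrawal, failure to wean by 35 days) and says "We will fit Cox proportional hazards models to the data to estimate the intervention effect and other covariate effects" on cause-specific hazards. SAP 6.4.5 item 5 keeps this, subject to sample size: "competing risk analysis will be performed using Cox proportional hazard model".

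**General survival analysis.** Protocol 5.1.4 offers it only as a possibility, beside negative binomial and median regression. SAP 6.4.5 item 4 reads "Perform survival analysis using cutoff at 35 days as censoring indicator" and names no model.

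**Who is included.** Under SAP 5.3 the efficacy analyses use the Full Analysis Set, while the survival analysis uses all randomized infants. SAP 6.1.1 keeps infants whose data collection stopped at withdrawal in the survival model only, as censored.

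**Checks.** SAP 6.4.2 covers continuous, binary and count models. It has no check for proportional hazards, and neither document gives a fallback if that assumption fails.

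**Schedule.** Protocol Table 4 gives five opioid levels in the rapid arm and eight in the slow arm. Appendix 10 shows the unescalated path: "Infant A stops opioid at step 5. Infant B continues opioid until step 8". On pace, Protocol 4.2.6 says "We will encourage clinical teams to wean study drug at least every 24 hours". Earlier weaning is allowed, and the team must wean or escalate by 36 hours.

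**The concern.** A Cox model summarises treatment as one constant multiplier on the rate of stopping opioid. Here the treatment instead removes three dose levels, which brings forward the usual earliest stopping time. Between the rapid and slow stopping times the ratio of rates should be very large. Later, the rapid-arm infants still on opioid are mostly those who escalated, while the slow arm is releasing infants who wean easily, so the ratio may fall below 1.

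When hazards are not proportional, the single Cox ratio is a weighted average whose weights depend on length of follow-up and on who is censored when. It also has no translation into days, so it cannot be compared with the 2.0-day difference the trial was designed around. This matters because the survival analysis is the only efficacy analysis that keeps infants withdrawn with no further data.

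**Working it through.** **1. The plan's own schedule.** The rapid arm's level after k steps is 100 − 15k percent, which reaches 25 at k = 5. The slow arm's is 100 − 10k, which reaches 20 at k = 8. This reproduces steps 5 and 8 in Appendix 10. Unescalated stopping times are:

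| Step length | Rapid | Slow |
|---|---|---|
| 12 h (allowed) | 5 × 0.5 = day 2.5 | 8 × 0.5 = day 4 |
| 24 h (encouraged) | day 5 | day 8 |
| 36 h (longest) | 5 × 1.5 = day 7.5 | 8 × 1.5 = day 12 |

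At any common pace without escalation, the slow-arm hazard is zero in the gap between the two columns.

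**2. The SD used as a benchmark.** SAP 3.4 gives 6.2 days. With a difference of 2.0 days, two-sided alpha 0.05 and 80% power, n per arm = 2 × (1.960 + 0.842)² × 6.2² / 2.0² = 151. The total is 302, the SAP's figure.

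**3. Simulation of both arms on Table 4.**
- From the documents: a failed step returns to the preceding level with a hold of at least 24 h; failure on placebo resumes the last opioid level; follow-up ends at day 35. Slow-arm escalation was set to 38% or 48%, the methadone and morphine figures that Protocol 3.3.4 reports for a 10% wean.
- Assumed: steps fixed at 24 h, 12-36 h (mostly 24 h) or 9-36 h; rapid-arm escalation risk per step 1.0 to 1.5 times the slow arm's; variation between infants in escalation risk from none to strong.

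One scenario in full (12-36 h steps, 48% of slow infants escalating, equal risk per step, variation between infants; SD 6.02; mean 11.83 days slow, 8.00 rapid). Hazards are per infant-day:

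| Days | Slow | Rapid | Ratio |
|---|---|---|---|
| 4-6 | 0.000 | 0.340 | effectively infinite |
| 6-8 | 0.067 | 0.297 | 4.44 |
| 8-9 | 0.445 | 0.226 | 0.51 |
| 9-10.5 | 0.271 | 0.202 | 0.74 |
| 10.5-12.5 | 0.218 | 0.167 | 0.77 |
| 12.5-15.5 | 0.171 | 0.139 | 0.81 |
| 15.5-20.5 | 0.111 | 0.105 | 0.94 |
| 20.5-35 | 0.070 | 0.065 | 0.93 |

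The Cox ratio for the same infants is 4.03, 2.70, 2.42 and 2.24 with follow-up cut at days 9, 12, 16 and 35.

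**4. Range over the 12 scenarios with SD 6.0 to 6.7.**
- Days 4-6: infinite or nearly so with 24 h or 12-36 h steps; 12 to 17 with 9-36 h steps.
- Days 8-9: 0.08 to 0.66. Days 9-10.5: 0.49 to 1.06. Later: about 0.6 to 1.1.
- Cox ratio: 2.2-4.0 with follow-up cut at day 9, 1.6-2.4 at day 35.
- Mean difference: 2.3 to 3.8 days in favour of rapid weaning.

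**5. Visibility at the target size.** In one scenario with 151 per arm (300 simulated trials), a log-rank test restricted to days 8-35 pointed towards the slow arm every time, significantly in 92%. It compares only infants still on opioid at day 8, so it shows crossing, not a benefit of slow weaning.

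**The case against.** Several stronger readings are tempting, and the documents do not support them.

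- *Both survival analyses use Cox.* Cox is named only for competing risks. Item 4 leaves the model open, and its wording already allows an analysis in days. The fault there is an unnamed model.
- *No slow-arm infant can stop while rapid-arm infants are stopping.* This holds only for unescalated weaning at about 24 h per level. Steps may be shorter and escalations are unlimited. At an SD near 6.2, 13-16% of slow infants (12-36 h steps) or 45-52% (9-36 h steps) stopped before day 8, and 17-35% of rapid infants stopped at or after day 8.
- *The schedule alone makes the hazards cross.* Crossing also needs near-uniform steps or variation between infants in escalation. It was not clear in scenarios with variable steps, no such variation and equal escalation risk, where the ratio after day 8 was mostly 1.1-1.9. Those scenarios have an SD of only 1.6-1.9 days, far below 6.2.
- *The hazard ratio is meaningless.* It stayed above 1 in every scenario and agreed in direction with the mean difference. It is an average that depends on follow-up.
- *The trial's conclusion is at risk.* The primary analysis is a linear mixed model on days truncated at 35, which makes no use of proportional hazards.

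It can also fairly be said that restricted mean time adds little: for infants with complete data the primary analysis already compares mean days up to 35. The gain is confined to withdrawn infants without further data, and restricted mean time still assumes that their censoring is non-informative. All of this stands and limits the point. It does not rescue proportional hazards, which failed in every scenario, including those without clear crossing.

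**Conclusion.** The point holds in limited form. Five levels against eight shifts the usual stopping time, so proportional hazards is not credible by design for the cause-specific Cox analysis, and no check or alternative is planned. That part rests on the documents' own schedule.

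The fall of the hazard ratio below 1 soon after day 8 rests on assumptions: step lengths, rapid-arm escalation, and enough variation between infants to match an SD near 6.2 days. Under those assumptions one Cox ratio (1.6-2.4 at day 35) averages values from 12 or more early on to 0.08-0.66 on days 8-9. Its size depends on follow-up and censoring and cannot be compared with 2.0 days. Its direction was not in doubt in any scenario, and the primary result is untouched. Final enrolment is not stated; 151 per arm is half the 302 target.

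**What to change.** - **SAP 6.4.5 item 4:** name the difference between arms in restricted mean time on opioid to day 35 (days, 95% CI), on all randomized infants, as the survival sensitivity analysis. State that it still assumes non-informative censoring at withdrawal.
- **SAP 6.4.5 item 5:** report cumulative incidence of successful weaning by arm at prespecified days, with withdrawal as a competing event, beside any cause-specific Cox result.
- **SAP 6.4.2:** add a proportional-hazards check. Treat any Cox hazard ratio as descriptive, or give it a time-varying treatment effect.

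The cost is a few sentences in the SAP; the data and the 35-day cutoff are unchanged. The downside is losing a single familiar hazard ratio as the summary. If outcome data by arm have already been seen, the amendment should say so.
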